1.2 Primary Study Endpoints

MDD composite which includes MDD screen positive for the universal screening arm (or concern in the targeted screening group), MDD identification, and MDD treatment engagement. Each of the primary study endpoints will be collected at the individual level by the school district by the end of the school year. No identifiable information will be collected by study staff.

Universal Group

- 1) Adolescents with PHQ-9 score ≥ 11 (screen Sept-March of the school year) or who at any point in the year exhibit behavior concerning for MDD prompting a SAP triage request, 2) Adolescents identified with MDD by SAP triage, and 3) Adolescents who successfully engage with at least one SAP recommendation

Targeted Group

1) Adolescents with behavior concerning for MDD prompting a SAP triage request, 2) Adolescents identified with MDD by SAP triage, and 3) Adolescents who successfully engage with at least one SAP recommendation

Concern for MDD based on a primary or secondary potentially MDD related SAP "incoming referral reason"

SAP triage is not diagnostic, so MDD identified based on recommendations for MDD related school or community services (e.g. mental health treatment services)

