1.3 Secondary Study Endpoints

The secondary endpoints listed below are individual level data points that will be obtained from the school district and/or SAP. No identifiable information will be collected by study staff.

MDD screen positive or MDD concern prompting Student Assistance Program triage

Universal screening arm: Adolescents who have a PHQ-9 score ≥ 11 (screening with the PHQ-9 is planned for September to March) or who at any point in the school year exhibit behavior concerning for MDD which prompts self or collateral request for SAP triage.

Targeted screening arm: Adolescents with behavior concerning for MDD which prompts self or collateral request for SAP triage at any point during the school year.

Suicidal adolescent (includes suicidal thoughts [positive response to PHQ-9 item 9], attempts and completed)

Universal screening arm: Patient health questionnaire positive response to question #9 re: suicidal thoughts, which requires management by the state-mandated school crisis plan or student self or collateral report of suicidal thoughts, which requires management by the state-mandated school crisis plan (source school district).

Targeted screening arm: Student self or collateral report of suicidal thoughts, which requires management by the state-mandated school crisis plan (source school district).

Any student suicide attempts or completed suicides shared with the school district will also be included.

MDD identification

Universal and targeted screening arms: Adolescents who are identified as having MDD based on triage by the school SAP team. As SAP triage is not diagnostic, MDD identified will be based on SAP recommendations for school or community services which are MDD related (e.g. mental health treatment services).

MDD treatment engagement

Universal and targeted screening arms: Adolescents who successfully engage with at least one SAP recommendation. This may be fulfilled by parental report that an appointment was successfully scheduled

The secondary endpoints listed below are aggregate data points by grade level that will be obtained from the school district and/or SAP. No identifiable information will be collected by study staff. Please

note, secondary outcomes may no longer be available due to COVID-19 school closures and cancellation of state standardized testing.

Standardized test scores (i.e. Keystone exams, PSAT, SAT/ACT)
Student school policy violations and/or suspensions
Missed school days
Grade point averages

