7.2.2 Randomization

We will randomize by grade levels within each school to receive either one-time universal screening (via PHQ-9) or targeted screening (current SAP process). For the schools included in the study, half of the schools (50%) will be randomized such that students in 9th and 11th grades will receive universal screening and students in 10th and 12th grades will receive targeted screening, and the other half (50%) will be randomized such that students in 9th and 11th grades will receive targeted screening and students in 10th and 12th grades will receive universal screening. Randomization will be done only for students whose parents do not signal an unwillingness to participate in the study (“opt out”). Students and study personnel will not be blinded to randomized group at each school site. Randomization will be done by grade level primarily for pragmatic reasons because many PA health-based screenings are grade-specific (e.g. hearing screen in 11th grade) and screenings for a grade occur at the same time. The study will be conducted within schools, but it is not a cluster randomized study, in which an entire school (cluster) is assigned to one of the study groups. A cluster randomized study was considered but ultimately not pursued because randomization within schools controls for (1) within-school (community) factors that may contribute to higher or lower rates of SAP referral, (2) differences in school sizes, and (3) potential differences in rates of parental opt out among schools. These benefits were balanced against the concern of potential contamination between study groups, whereby those in the targeted screening group may benefit from the school-wide push to conduct universal screening.

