7.2.4 Targeted Screening Arm (Current Process – Control)

Students randomized to the targeted screening arm will complete their routine school-based screenings. Students will be followed through the academic year for SAP triage intakes initiated by the standard pathway (concern by teachers, nurse, parent, peer, or self-referral), any referrals and treatment engagement.

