16.4 Availability of medical or psychological resources

It is not anticipated that medical or psychological resources will be needed on site, given that study procedures are minimal risk. However, students with suicidal intent will receive immediate evaluation and referral to emergency care as per current school protocols. PA schools are required to have a plan to address suicidal students. A QPR trained staff member will be available at the time of screening. Students with a PHQ-9 score ≥ 11 will proceed to Student Assistance Program triage as per the standard of care by which students exhibiting concerning behavior (outbursts, declining grades) would be referred for assessment.

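### Step 1 of the primary composite applies a referral-reason filter that a PHQ-9 score of 11 or more bypasses, so an identified and engaged student may count only in the universal arm; a route-neutral sensitivity analysis should be added

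*Combined protocol and SAP*

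**What the plan says.** All references are to the amended (14-school) protocol in the combined document.

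- **Step 1, universal arm (1.2).** There are two routes: "Adolescents with PHQ-9 score ≥ 11 (screen Sept-March of the school year) or who at any point in the year exhibit behavior" concerning for MDD that leads to a Student Assistance Program (SAP) triage request.
- **Steps 1 and 2, targeted arm (1.2).** "1) Adolescents with behavior concerning for MDD prompting a SAP triage request, 2) Adolescents identified with MDD by SAP triage". The behaviour route is the only way through step 1.
- **Coding of the behaviour route (1.2).** "Concern for MDD based on a primary or secondary potentially MDD related SAP" incoming referral reason. No list of qualifying reasons is given.
- **Step 2, both arms (1.2).** "SAP triage is not diagnostic, so MDD identified based on recommendations for MDD related school or community services".
- **Step 3, both arms (1.3).** "Adolescents who successfully engage with at least one SAP recommendation. This may be fulfilled by parental report that an appointment was successfully scheduled".
- **Scoring (8.3).** The composite is binary and needs all three elements.
- **Secondary outcomes (1.3, 8.3).** Identification and engagement are also analysed separately. Each has one definition for both arms, with no stated referral-reason condition.
- **Follow-up of the targeted arm (7.2.4).** "Students will be followed through the academic year for SAP triage intakes initiated by the standard pathway".

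**The concern.** Steps 2 and 3 describe the care a student received and are the same in both arms. Step 1 depends on how the student came to triage, and it is not the same. The incoming reason records what someone noticed before triage, not what triage found.

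In the targeted arm, a student whose recorded reason is off the list fails step 1 even if SAP then recommends mental health treatment and the student takes it up. In the universal arm, a student with the same course passes step 1 if screened with a score of 11 or more. Nothing in 1.2, 1.3 or 8.3 re-codes the first student.

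This is separate from the intended effect of screening. Students whom the PHQ-9 brings to care and who would otherwise have been missed are real gain. The issue is limited to students who would reach triage, recommendation and engagement in either arm but are counted in only one. For them the difference lies in the counting, and it inflates the odds ratio.

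**Working it through.** **1. One student, three settings.** The incoming reason is off the list, SAP recommends mental health treatment, and the student engages.

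| Setting | Step 1 | Steps 2 and 3 | Composite |
|---|---|---|---|
| Targeted arm | fails | met | 0 |
| Universal arm, PHQ-9 ≥ 11 | met by score | met | 1 |
| Universal arm, PHQ-9 < 11 or not screened | fails | met | 0 |

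The filter also binds the behaviour route in the universal arm. The discrepancy is therefore confined to students who screen positive.

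**2. The plan's own figure.** Section 8.2 states more than 99% power for 3% versus 6% with 4,820 per group and two-sided 5%. A two-proportion test without clustering gives more than 99.99%, so the figure reproduces. It is not in dispute.

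**3. Size of the counting difference under no true effect.** The inputs are:
- n = 4,820 per arm (8.2).
- p = 4% in both arms, the true rate of being recommended MDD-related services and engaging. This is an assumption, set between the plan's 3% and 6%.
- r, the share of those students whose incoming reason is not on the list. It is not in the documents, so it is varied.
- s, the share of those students who would be screened and score 11 or more in the universal arm. It is not in the documents; 60% is used, with 40% to 80% as the range.

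Counted rates:
- targeted T = p(1 − r)
- universal U = p(1 − r) + p·r·s
- difference U − T = p·r·s, which is never negative
- z = (U − T) / √(2·m(1 − m)/n), with m = (T + U)/2

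Example, r = 25%, s = 60%: T = 0.04 × 0.75 = 3.0%. U = 3.0% + 0.04 × 0.25 × 0.60 = 3.6%. m = 0.033. SE = √(2 × 0.033 × 0.967 / 4,820) = 0.00364. z = 0.006 / 0.00364 = 1.65. OR = (0.036/0.964) / (0.030/0.970) = 1.21.

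| r (s = 60%) | Targeted | Universal | OR | z |
|---|---|---|---|---|
| 10% | 3.60% | 3.84% | 1.07 | 0.62 |
| 25% | 3.00% | 3.60% | 1.21 | 1.65 |
| 30% | 2.80% | 3.52% | 1.27 | 2.02 |
| 50% | 2.00% | 3.20% | 1.62 | 3.70 |

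With s = 60%, z reaches 1.96 at r of about 29%. With s = 40% the threshold is about 40%, and with s = 80% about 23%.

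**4. Influences on the size.**
- Students who do not assent (5.3.3.2) and universal-arm students at the two schools where screening could not be completed (7.1) have no bypass. If, for illustration, one in six affected universal-arm students were unscreened, s = 60% would become 0.60 × 5/6 = 50%, and the threshold would rise to r of about 34%.
- Applying the 15% attrition of 8.1 gives 9,640 × 0.85 / 2 = 4,097 per arm. The threshold at s = 60% becomes about 31%.
- Correlation within school-by-grade groups is ignored here; positive correlation would lower z.

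**5. If screening does work.** Suppose the counted rates are the planned 3% and 6% (OR 2.06). Route-neutral rates are then 0.03/(1 − r) in the targeted arm and 0.06 + [0.03/(1 − r)]·r·(1 − s) in the universal arm. For s between 50% and 80%, the route-neutral OR is 1.87 to 1.91 at r = 10% and 1.68 to 1.75 at r = 20%. Power stays above 99%. The cost is an overstated odds ratio, not lost power.

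**The case against.** The strongest reply is that little is at stake and part of it is already checked. The filter accepts a primary or a secondary reason that is only potentially related to MDD, so few engaged students may fall outside it. Identification and engagement are each analysed separately with arm-neutral definitions. Step 2 is not diagnostic, so step 1 is what makes the composite specific to depression. A universal-arm student scoring 11 or more has measured depressive symptoms, and recognising them is part of what screening is for.

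Most of this stands as a limit on size. It does not remove the asymmetry. The two separate outcomes do not determine the joint one: identification includes students who never engage, and engagement means any one SAP recommendation.

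A reader might infer three stronger points that the documents do not support.

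- **That ordinary referral reasons fail the filter.** Section 16.4 says "students exhibiting concerning behavior (outbursts, declining grades) would be referred for assessment", but it offers these as typical concerning behaviour behind a standard referral. Section 2.3 links depressive symptoms to lower grades. They read more naturally as reasons that would pass.
- **That unblinded staff decide which reasons qualify.** Section 7.2.2 says "Students and study personnel will not be blinded to randomized group at each school site". It does not say who classifies referral reasons, or when.
- **That the filter alone would produce a positive trial.** This holds only if r is large, and the documents give no value for r.

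**Conclusion.** The asymmetry is real. It follows from 1.2 read with the scoring rule in 8.3, and under no true effect it can only favour universal screening, provided the list is applied alike in both arms. Its size is unknown and may be small. Under the stated assumptions (p = 4%, s = 60%, 4,820 per arm, no clustering), it gives an odds ratio of 1.07 if one in ten identified and engaged students has an unlisted reason, and 1.21 without nominal significance if one in four has. It could pass for a treatment effect on its own only from about 30%. The text supports neither calling the primary endpoint invalid nor saying that the filter would decide the trial. It does support a missing robustness check that uses data already being collected.

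**What to change.** In 8.3, pre-specify one sensitivity analysis of the primary outcome, with the same mixed logistic model. Score it 1 when a student is identified with MDD and engaged, whatever the entry route: any SAP triage request in either arm, or PHQ-9 ≥ 11 in the universal arm. Judge MDD-relatedness at step 2 only, by one list of recommended services used in both arms.

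In 1.2, give the list of MDD-related incoming referral reasons and fix it before outcomes are linked to arm. Report the route-neutral odds ratio and confidence interval beside the primary one. Tabulate by arm the identified and engaged students who fail step 1, which gives r directly in the targeted arm. The primary conclusion need not depend on both analyses agreeing.

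The cost is some wording and one extra model, since intakes, referrals and engagement are already tracked for all enrolled students. The drawback is that the route-neutral version admits some non-depression referrals in both arms. It is therefore less specific to depression and belongs beside the primary analysis, not in its place.

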1.3 Secondary Study Endpoints

The secondary endpoints listed below are individual level data points that will be obtained from the school district and/or SAP. No identifiable information will be collected by study staff.

MDD screen positive or MDD concern prompting Student Assistance Program triage

Universal screening arm: Adolescents who have a PHQ-9 score ≥ 11 (screening with the PHQ-9 is planned for September to March) or who at any point in the school year exhibit behavior concerning for MDD which prompts self or collateral request for SAP triage.

Targeted screening arm: Adolescents with behavior concerning for MDD which prompts self or collateral request for SAP triage at any point during the school year.

Suicidal adolescent (includes suicidal thoughts [positive response to PHQ-9 item 9], attempts and completed)

Universal screening arm: Patient health questionnaire positive response to question #9 re: suicidal thoughts, which requires management by the state-mandated school crisis plan or student self or collateral report of suicidal thoughts, which requires management by the state-mandated school crisis plan (source school district).

Targeted screening arm: Student self or collateral report of suicidal thoughts, which requires management by the state-mandated school crisis plan (source school district).

Any student suicide attempts or completed suicides shared with the school district will also be included.

MDD identification

Universal and targeted screening arms: Adolescents who are identified as having MDD based on triage by the school SAP team. As SAP triage is not diagnostic, MDD identified will be based on SAP recommendations for school or community services which are MDD related (e.g. mental health treatment services).

MDD treatment engagement

Universal and targeted screening arms: Adolescents who successfully engage with at least one SAP recommendation. This may be fulfilled by parental report that an appointment was successfully scheduled

The secondary endpoints listed below are aggregate data points by grade level that will be obtained from the school district and/or SAP. No identifiable information will be collected by study staff. Please

note, secondary outcomes may no longer be available due to COVID-19 school closures and cancellation of state standardized testing.

Standardized test scores (i.e. Keystone exams, PSAT, SAT/ACT)
Student school policy violations and/or suspensions
Missed school days
Grade point averages
Grade advancement or graduation rates

Additional data points to be obtained for subgroup analyses include:

- At the individual level:
 - Sex - male or female
 - Ethnicity - Hispanic vs. non-Hispanic
 - Race - white, black or other
 - Urban/rural – students will be categorized as enrolled in urban or rural school districts based on the definition applied by The Center for Rural PA, a Legislative Agency of the PA General Assembly for the district

- At the aggregate level, the following variables will be collected:
 - District socioeconomic status
 - School size – school enrollment. Data will be obtained from school districts based on enrollment as of October 1 of the RCT
 - Ratio of guidance counselors/students – The ratio of counselors to students will be obtained from each school district
 - School-based mental health services – schools will be categorized by the availability of school-based mental health services (yes vs. no) based on information obtained from each school district.

We need to collect data at the individual level for 3 main reasons. First, we expect approximately 20% of students to opt out from the study, with opt out rates varying by grade. Aggregate data would necessarily include outcomes for students who are not enrolled in the study. This is particularly problematic for the universal screening group because students who opt out will not be offered the depression screening tool (PHQ-9). Second, we need to obtain gender and race/ethnicity to conduct important planned secondary analyses (subgroup analyses) that will examine efficacy of universal screening by these groups. In particular, we expect that females and minority students will have much higher rates of major depression disorder identified in the universal screening group. Third, in the universal screening group, we will be able to link responses to the PHQ-9 to outcomes, which will allow for estimation of important measures such as the false positive rate of the PHQ-9 (score ≥ 11 , but SAP process determines no further referrals are needed). These measures will inform decision-making regarding the potential for implementation of the intervention (in other schools) should the results of the trial ultimately show efficacy.

2.0 Background

2.1 Scientific Background and Gaps

The prevalence of annual major depressive disorder (MDD) episodes among US adolescents rose from 8.3% in 2008 to 12.5% in 2015.¹ Close to 30% of adolescents with MDD reported suicidality in the prior year, with more than one in ten making a suicide attempt.² As a result, suicide was the 2nd leading cause of death among youth 10-24 years of age as of 2014.³ Baseline data from HealthyPeople.gov

found that only 2.1% of adolescent primary care office visits included depression screening in the years 2005-2007.⁴ Inequalities were reported for women who are three times more likely to have MDD, but less likely to be treated than males.^{1,2,6} In response to the growing mental health crisis, the US Preventive Services Task Force (USPSTF) endorsed universal screening for adolescent MDD in primary care in 2009.^{7,8} The HealthyPeople.gov 2020 goal is a 10% increase in screening to a rate of 2.3%, which fails to address this adolescent public health crisis.⁴ The USPSTF universal MDD screening recommendation was based on evidence that treatment of MDD is associated with moderate benefit.^{7,8} While most experts in family medicine, pediatrics, psychology and child psychiatry agree that surveillance of adolescents at high-risk for MDD is warranted, the USPSTF updated their recommendations in 2016 with a call to address several knowledge gaps:

- 1) Does screening increase the proportion of adolescents identified with MDD?
- 2) What are the benefits and unintended consequences of MDD screening for subgroups: age, sex, race, ethnicity and socioeconomic status (SES)?
- 3) What are the benefits and unintended consequences of screening in nonclinical settings?⁸

We propose that schools may provide an effective setting to conduct universal MDD screening. While over half of US adolescents do not have annual preventive health visits most attend school.⁹ The regular contact with schools compared to contact with the medical setting has been used to advocate for many school-based universal health screenings that impact academic success (e.g. vision, hearing). However, while current school screenings address multiple physical health domains, none address mental health.¹⁰ Targeted mental health screening is the current school process for students who display signs concerning for MDD and results in referral to the school's Student Assistance Program (SAP). SAP operates in all 500 Pennsylvania school districts and functions similar to a triage service by assessing symptom severity, and then if appropriate, providing referrals to school or community-based mental health resources.¹¹ Students may self-refer, but all other SAP referrals depend upon a student exhibiting concerning behavior that is detected by school staff, peers or parents, which results in a targeted screening process with obvious limitations.

2.2 Previous Data

Our research team is acutely aware of the concerns the topic of adolescent depression screening may raise among school staff, providers, parents and adolescents. We have had ample opportunity in our pilot work to discuss and address many of these issues as outlined below. First, from April-Sept 2016 we conducted eight focus groups (7-10 participants each, n=62) to better understand the perspective of key stakeholders regarding Whole Child Health, specifically the importance of both physical and mental wellness. These focus groups included 2 parent groups, 2 school nurse groups, 2 groups of school teachers and administrators and 2 groups of medical providers (pediatrics and family medicine). The work was funded by the Penn State Social Science Research Institute-Children, Youth and Families Consortium. Participant conversations were instrumental in shaping the current proposal. In addition, following the aforementioned focus groups, we conducted a Community Engagement Studio in August 2017 funded by the Penn State Center for Translational Science Institute. These 2 hour sessions are specifically intended to inform grant proposals that depend upon successful community engagement. Participant perspectives ranged from adolescent to parent, school staff, the leaders of two mental health and suicide prevention organizations (Aevidum and the Jana Marie Foundation), a Behavioral Health Managed Care company representative and the project director of Pennsylvania's Garrett Lee Smith Youth Suicide Prevention Grant in addition to our Penn State Research team.

